#### 7.7 *Safety Monitoring Board:*

An independent data safety monitoring board (DSMB) who is unaffiliated with the protocol and with no conflict of interest will be appointed. During the course of the study, the independent safety monitoring board will review cumulative study data twice per year to evaluate safety, study conduct and integrity of the trial. At each visit, vital signs, adverse events/side effects, concomitant medications, and pertinent lab values will be recorded. The independent safety monitoring board may also be requested to review data as needed if stopping criteria are met or if safety issues arise that the Sponsors or Principal Investigator would like the independent safety monitor to address. The independent safety monitoring board will be notified in the case that un-blinding occurs. The independent safety monitoring board will conclude each review with their recommendation to the sponsors as to whether the study should continue without change, be modified, or terminated. The sponsor will submit the written recommendations of the independent safety monitoring board to the IRB upon receipt.

The independent data safety monitoring board consisting of [name], UAB Department of Medicine, [name], CRNP, Children's of Alabama, [name], Children's of Alabama, and [name], PhD, Department of Molecular and Clinical Medicine, Sahlgrenska University Hospital, Gothenborg, Sweden, will review data after the 6 months visit to assess benefit of the study. The board may suspend the study at any time if felt needed to evaluate safety further.

#### 7.8 *Stopping Rules for Premature Termination of the Study*

- 1.) Any death related to the study medication
- 2.) By request of the independent data safety monitoring board

#### 8.0 *Data Processing and Management:*

All participant data will be obtained and recorded in individual files that will be stored in a secured file cabinet within a locked office. Upon study entry, all participants will be given a unique identifier to be used through the entirety of the study and this too will be maintained in a locked file cabinet in secured office. Following each study visit, the data obtained will be entered into a database using the study participants' unique identifiers.

All other personal data will be omitted from electronic records. At the close of the study, any missing data will be verified with chart review. Only authorized study personnel will have access to patient data. Laboratory results will be transcribed from laboratory printouts to the Access database.

#### 9.0 Data Analysis:

Baseline demographic and other (e.g., weight) characteristics will be compared between the treatment groups using t- and chi-square tests (or their non-parametric equivalents) for continuous and categorical variables, respectively, in order to demonstrate the success of the randomization process. The primary outcome measure is C-peptide level, which is measured at multiple time points during the study. As is standard practice, the post-stimulus area under the curve (AUC) will be calculated in addition to mean and peak values. The main analysis will focus on a comparison of the baseline and the > 12-month post baseline C-peptide measurements. Analysis of covariance will be used to compare changes in C-peptide levels between the treatment groups. For these analyses the 12-month post baseline measurement will serve as the dependent variable; there will be two independent variables: (1) a binary variable for treatment group and (2) the baseline C-peptide measurement. This is a standard analytical approach for study designs of this type. Given that GABA may affect  $\alpha$ -cell glucagon secretion, possible changes in the circulating concentrations of this hormone will be appraised. In the unexpected event that the treatment groups are not similar with respect to specific demographic and other characteristics, these measurements will also be considered as potential confounders in the aforementioned analysis. A similar analytical approach will be used for the other study outcomes of interest besides glucagon, i.e., hemoglobin A1C, insulin dose/kg body weight/24 hours. Mixed statistical models will be used to conduct longitudinal analyses of C-peptide and hemoglobin A1C measurements, and daily insulin requirements, incorporating all three measurements. All analyses are conducted on an intention to treat basis.

Adverse events and other safety data will be summarized descriptively.

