
Primary Endpoint:
 
 
Evaluate the effect of GABA and GABA + GAD-alum combination on pancreatic beta cell function, as measured by meal stimulated C-peptide secretion levels compared to age-matched placebo controls, before and after one year of treatment.
 
 
Secondary Endpoints:
 
 
Evaluate the effect of GABA and GABA + GAD-alum combination on autoimmune diabetes autoantibodies: GAD-65, ICA512, and Zinc Transporter 8(ZnT8A) and the effect on HbA1c, fasting and stimulated glucose & glucagon levels, fasting C-peptide and the amount of daily insulin usage by participants, from baseline through subsequent visits
 
Evaluate the safety of GABA and GABA/GAD-alum combination
 
 
Safety The safety assessment includes observation of reactions at the injection site, occurrence of adverse events (AEs), laboratory measurements, neurological assessments, and limited physical examinations.
 
Sample size: The sample size for the proposed study is 110 children; 30 in the treatment group of active GABA and active GAD-alum, 43 in the treatment group receiving active GABA and placebo GAD-alum, and 37 in the placebo group. For the primary comparison of the 12-month post-baseline C-peptide measurements between these groups, assuming an <math>\alpha</math> of 0.05 and a mean (SD) C-peptide AUC of 1.0 (0.4) this sample size yields a ~97% power to detect a 50% difference. Adverse events and other data will be summarized descriptively.

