A total of 110 patients, with 30 in the GABA + GAD-alum group 43 in the GABA + placebo GAD-alum group, and 37 in the placebo GABA and placebo GAD-alum group will be enrolled. The study will be double-blinded with randomization under the stewardship of the Children’s Hospital research pharmacist. Subjects will be randomized to one of the three treatment groups in a 1:1:1 ratio using a pre-set randomization list (generated by using a computerized procedure) known only to the un-blinded pharmacist.

The patients will be followed for a total study period of 12 months which includes 5 visits to the clinic.

See table 1 below for an overview of randomization groups and study visits.

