Suspected unexpected serious adverse reactions (SUSARS) will, if required, be un-blinded for reporting to regulatory agencies and ethics committees, Diamyd Medical, Janssen/JDRF (or its designees) will be supplied with the necessary information to break the study blind for individual patients as required for regulatory reporting purposes. However, the investigator, sponsor, and study team will be kept blinded to the treatment allocation.

The study blind will be broken when all patients have completed the study, and all data for this period has been entered into the database and locked. One randomization list is retained by the un-blinded pharmacist. After the database lock, the results will be analyzed and un-blinded where after a 12 month analysis will be performed.

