- 14.) *Cell Activation and Inflammation Markers*: Since GABA has been shown to possibly improve inflammation and cellular activity in animal studies we will evaluate for inflammatory and cell markers at varied points in the study. We propose a detailed immune analysis strategy that has 3 arms: (1) analysis of functional CD4 and CD8 subsets (effector vs regulatory) We will perform immunophenotyping studies of the peripheral CD4 and CD8 subsets at baseline and at the 5 and 12 month study visits with monoclonal antibodies specific for CD3, CD4, CD8, CCR4, CCR5, CCR7, CXCR3, CXCR5, CD25, CD28, CD38, CD39, CD45RA, CD45RO, CD62L, CD127, Helios, Foxp3, and PD-1 [BD Biosciences, R&D Systems, eBiosciences] Intracellular cytokine staining of PMA/Ionomycin-anti-CD3/CD28, GAD65 peptivator (Miltenyi Biotec), and tetanus toxoid-stimulated cells will also be examined with monoclonal antibodies to IFN- $\gamma$ , TNF- $\alpha$ , IL-13, IL-10, and IL-17A (BD Biosciences, eBioscience) We expect to observe a decrease in CD4 and CD8 T cell effector cell populations secreting IFN- $\gamma$  and a concomitant increase in CD4 Treg cells (CD4+/CD25+/FoxP3+) that secrete IL-10. Human multi-color flow cytometric analysis will be performed as previously described. (2) functional assays of T cell responses after GABA exposure. we will perform T cell proliferation (CFSE dilution or cell counting kit-8 assays and primary recall assays as previously described to determine if GABA treatment has an effect on decreasing effector cytokine production of CD4 and CD8 T cells and a concomitant increase in Treg cells as described above. Briefly, PBMCs will be purified from fresh blood and stimulated with PMA/Ionomycin. Dynal beads conjugated with anti-CD3 and anti-CD28, GAD65 Peptivator peptides and tetanus toxoid. Supernatants will be collected and the levels of cytokines and chemokines produced by activated T cells will be determined with a Milliplex Human Cytokine/Chemokine Magnetic Bead panel (3) monitoring of serum autoantibody expression {both number of autoantibodies expressed, as well as changes in titer} over the course of the study. The presence and number of positive autoantibodies correlates not only with diabetes diagnosis, but also with degree of beta cell destruction and progression of disease. We are planning subgroup analyses to see if GABA and or GABA/GAD combination have different efficacies based on antibody titers and number of positive antibodies (i.e. participants who are likely to be slow- or fast- progressors). We also want to determine if the number of positive autoantibodies per participant changes, either increases, or decreases, with GBA therapy. Obviously we understand that autoantibodies are not directly pathologic to beta cells, but they may serve as an epiphenomena/surrogate marker for the degree of beta cell destruction. We also propose to add the pro-insulin/C-peptide ratio as a marker of beta cell health. We have arranged with our Metabolism Core Lab at UAB to run the proinsulin levels. For participants who have already completed some study visits, these assessments can still be run from the samples previously collected. HLA (Human Leukocyte Antigens will be performed per [name]. This will be done on samples already collected for the Cell Activation and Inflammatory Markers. The genes in HLA are reported to account for 40-50% of the familial aggregation of Type 1 diabetes. There are certain genes within the HLA typing that have been shown to cause a rapid decrease in  $\beta$ -cell function, whereas other genes seem to have a more gradual destruction. We feel this information can be most beneficial in our research concerning how Type 1 progresses and does the HLA typing effect how these patients respond to the GABA/GAD therapy. Diamyd agreed to fund the additional cost of the research.

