#### 10.0 Power Calculations:

The sample size for the proposed study is 95 children; 25 in the active GABA/GAD-alum treatment group, 35 in the GABA/Placebo Gad-alum group, and 35 in the placebo group. For the primary comparison of the 12-month post baseline C-peptide measurements between these groups, assuming an  $\alpha$  of 0.05 and a mean (SD) C-peptide AUC of 1.0 (0.4) this sample size yields a ~97% power to detect a 50% difference.

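### Section 9.0 ties extra covariates in the primary ANCOVA to observed baseline imbalance, with no threshold or entry rule; fixing age in advance is the better method at almost no cost

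*Combined protocol and SAP*

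**What the plan says.** Section 9.0 makes 12-month C-peptide the dependent variable and allows two independent variables: a treatment indicator and "2) the baseline C-peptide measurement". It then adds a fallback. "In the unexpected event that the treatment groups are not similar with respect to specific demographic and other characteristics", the plan says, "these measurements will also be considered as potential confounders in the aforementioned analysis".

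Earlier in the same section, t- and chi-square tests (or non-parametric equivalents) are named for comparing baseline characteristics. Their stated purpose is to show that randomization worked. Weight is the only variable given as an example. No significance level or imbalance threshold is stated, and nothing connects the test results to entry of a covariate.

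On age, the synopsis and Section 4.2 both word the primary endpoint as "compared to age-matched placebo controls". Section 5.3 admits patients aged 4 to 18. Section 5.6 describes allocation "using a pre-set randomization list (generated by using a computerized procedure") and mentions no matching or stratification by age. Date of birth is collected at baseline screening (Section 6.7, item 10).

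**The concern.** Two things do not fit together. First, an imbalance-triggered adjustment chooses covariates by how unequal the arms happen to look, not by how strongly the covariate predicts the outcome. It therefore gives up most of the precision that a prognostic covariate offers, and here it also lacks the rule that would make it reproducible: what counts as dissimilar, when a variable that is considered is actually entered, and which model is then primary. Second, the endpoint wording promises comparability on age that neither the randomization nor the model provides.

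At stake are a modest amount of precision and a clear statement, made before unblinding, of which covariates the primary model contains.

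**Working it through.** **The plan's own figure.** Section 10.0 states about 97% power for a 50% difference (0.5) with SD 0.4, α 0.05 and arms of 25/35/35. The normal approximation, Φ(0.5 / (0.4·√(1/n₁+1/n₂)) − 1.96), gives 99.8% for 25 v 35 and 99.95% for 35 v 35. With the synopsis sizes of 30/43/37 it gives 99.9% (30 v 37) and 99.98% (43 v 37). The stated 97% is not reproduced on a plain reading. That, and the two sets of arm sizes, are separate matters; this point does not rest on them.

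**Inputs.** From the documents: arms 30/43/37 (synopsis), α 0.05, SD 0.4, planned difference 0.5. Assumptions: two-sided tests, pairwise contrasts against placebo, no dropout, age explaining a share r = 0, 5% or 20% of the variance left after baseline C-peptide, and a true difference of 0.25 (half the planned one). Section 10.0 words 0.4 as the SD of C-peptide AUC itself, that is, a total SD. Both readings are therefore shown, the second with a baseline/12-month correlation ρ of 0.5 or 0.7 (assumption):

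- 0.4·√(1 − 0.5²) = 0.346
- 0.4·√(1 − 0.7²) = 0.286

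**Formula.** With N = n₁ + n₂ and k covariates (1 without age, 2 with), Var = σ²(1 − r)(1/n₁ + 1/n₂)(N − 3)/(N − 3 − k), taking r = 0 when age is left out. Degrees of freedom are N − 2 − k. Power comes from the noncentral t with noncentrality Δ/√Var.

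**Example, 30 v 37, σ = 0.4, Δ = 0.25.** 1/30 + 1/37 = 0.06036.

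- Without age: Var = 0.16 × 0.06036 × 64/63 = 0.00981, noncentrality 2.524, 64 df, power 70.1%.
- With age at r = 20%: Var = 0.16 × 0.8 × 0.06036 × 64/62 = 0.00798, noncentrality 2.799, 63 df, power 78.7%.

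**Power (%) at Δ = 0.25** (changes taken before rounding):

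| Residual SD | Pair | No age | Age, r = 0 | r = 5% | r = 20% | Change, points |
|---|---|---|---|---|---|---|
| 0.400 | 30 v 37 | 70.1 | 69.3 | 71.6 | 78.7 | −0.7 / +1.5 / +8.7 |
| 0.400 | 43 v 37 | 78.1 | 77.5 | 79.6 | 85.9 | −0.6 / +1.5 / +7.8 |
| 0.346 (ρ = 0.5) | 30 v 37 | 81.9 | 81.2 | 83.2 | 88.9 | −0.6 / +1.3 / +7.1 |
| 0.346 (ρ = 0.5) | 43 v 37 | 88.4 | 88.0 | 89.6 | 93.9 | −0.4 / +1.1 / +5.5 |
| 0.286 (ρ = 0.7) | 30 v 37 | 93.6 | 93.2 | 94.3 | 97.1 | −0.4 / +0.7 / +3.5 |
| 0.286 (ρ = 0.7) | 43 v 37 | 96.9 | 96.7 | 97.4 | 98.9 | −0.2 / +0.5 / +2.0 |

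With the Section 10.0 sizes, 25 v 35 at σ = 0.4 changes by −0.8 to +8.8 points. Simulation (40,000 trials per cell, residual SD 0.4 and ρ = 0.5) agrees within 0.4 points, with type I error of 4.9–5.1% when age is fixed in the model.

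**At the planned difference of 0.5**, power without age is 99.87% (30 v 37) and 99.98% (43 v 37), so age adjustment can move it by only about 0.1 point.

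**Break-even.** Ignoring the lost degree of freedom, the variances match at r = 1/(N − 4): 1/63 = 1.6% and 1/76 = 1.3% of residual variance.

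**How a trigger would behave.** Suppose dissimilar meant p < 0.05.

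- For one pair of arms, chance alone would flag at least one of 5 independent variables with probability 1 − 0.95⁵ = 23%, and one of 10 with probability 1 − 0.95¹⁰ = 40%.
- A true age imbalance of 0.4 SD would be flagged only 36% (30 v 37) to 42% (43 v 37) of the time.
- In simulation (43 v 37, effect 0.5 residual SD, age partial correlation 0.3, or 9% of residual variance), power was 0.59 without age, 0.59 with the trigger and 0.63 with age fixed. The trigger recovered almost none of the gain. Its type I error was 0.051, and 0.042 at a partial correlation of 0.5.

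**The case against.** The strongest reply is that the primary model is largely fixed already. Two terms are named, and the fallback is reserved for an event the plan does not expect. The comparison tests are named, and age would naturally fall among the demographic variables compared. Analysts stay blind until database lock (Section 5.8). All of this stands. A reader might infer that the primary model is open, or that no method of baseline comparison exists; the text supports neither. What is missing is the threshold and the link to covariate entry. Blinding limits discretion but does not supply that rule, and Section 5.8 places the 12-month analysis after unblinding: "After the database lock, the results will be analyzed and un-blinded where after a 12 month analysis will be performed".

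A second reply is that no passage says age predicts C-peptide decline. Section 6.7, item 14, gives more support to autoantibodies ("The presence and number of positive autoantibodies correlates not only with diabetes diagnosis, but also with degree of beta cell destruction") and to HLA type. This also stands, and it is why the age effect is shown as a range from zero. Age is still a reasonable choice: it is the one characteristic that the endpoint wording itself names, and it is already collected. Item 14 plans the antibodies for subgroup analyses and asks whether HLA type affects response; it proposes neither as a primary-model covariate.

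A third reply is that the age-matching phrase is loose wording in a randomized trial. That is probably so, but it sits in the primary endpoint and describes something the design does not do.

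**Conclusion.** The point holds as a low-priority improvement in method. Fixed adjustment for age is better than adjustment triggered by observed imbalance, and the endpoint wording should agree with the design.

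Three stronger readings are not supported. The treatment estimate is not biased: randomization protects it with or without age. Type I error is not shown to be inflated: a mechanical trigger held it at about 5% or below. Free choice among eight covariate sets after seeing results raised it to about 8–9% in simulation, but nothing in the documents suggests that practice. The planned power is not at risk either, since nothing material changes at 0.5.

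Any power benefit depends on two assumptions: a true effect smaller than planned, and a prognostic age effect. The gain approaches 9 points only at the 20% extreme with 0.4 read as the residual SD; at 5% of residual variance it is about 0.5 to 1.5 points.

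**What to change.** In Section 9.0, pre-specify the primary ANCOVA with treatment, baseline C-peptide and age at baseline as a continuous variable. Move any imbalance-triggered adjustment to a labelled sensitivity analysis whose variables are named before unblinding. Report baseline characteristics descriptively. In the synopsis and Section 4.2, delete the age-matching wording, or describe the matching if it is intended.

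Section 6.7, item 14, indicates that some participants have already completed visits, so this is a mid-trial amendment and should be dated before database lock and unblinding. It needs no new data and no extra patients. It costs one degree of freedom: at most about 0.7 power points at 30/43/37, or 0.8 at 25/35/35, if age turns out not to be prognostic.

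This change does not by itself settle the primary model. The binary treatment variable for three arms and the choice among C-peptide AUC, mean and peak need their own decisions.

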#### 10.0 Power Calculations:

The sample size for the proposed study is 95 children; 25 in the active GABA/GAD-alum treatment group, 35 in the GABA/Placebo Gad-alum group, and 35 in the placebo group. For the primary comparison of the 12-month post baseline C-peptide measurements between these groups, assuming an  $\alpha$  of 0.05 and a mean (SD) C-peptide AUC of 1.0 (0.4) this sample size yields a ~97% power to detect a 50% difference.

#### 11.0 Administrative and Regulatory Procedures

Any regulatory requirements must have been met before starting the study. The sponsor will apply for the regulatory approval to the appropriate authorities. Study sites, facilities, laboratories and all data (including source data) must be made available for inspection by the authorities.

The University of Alabama at Birmingham IRB will be utilized for this study.

The study will be managed and conducted according to the latest international (ICH) guidelines for Good Clinical Practice (GCP).

The CRFs and all medical records upon which the CRFs are based (source data) must be kept for at least 10 years after completion of the study.

The investigator must ensure that patient's confidentiality will be maintained. CRFs or other documents submitted to the study team or Diamyd Medical (or its designee) should only identify patients by their initials and patient number. The investigator should keep a separate log of patient codes and names.

The patient's completed Consent Forms should be retained by the investigator in strict confidence.

The investigator must keep a confidential screening log, recording all patients who were screened, whether they were enrolled or not, and a separate Patient Identification List showing code numbers, names, and dates of birth to allow unambiguous identification of each patient included in the study.

In order to conduct this study consistent with established research principles and ICH-GC guidelines, there may be site visits conducted during the study to evaluate study conduct. All sites will be monitored for patient enrollment, compliance with protocol procedures, completeness and accuracy of data entered on the case report forms (DRFs) and the occurrence and reporting of AEs and SAEs

### 12.0 Publication Strategy:

Data obtained from this study will be presented as a poster or oral presentation at the Pediatric Endocrine Society meeting (formerly Lawson Wilkins Society). Thereafter, results will be culminated and submitted for review to a first-tier, peer-reviewed journal.

